## 1.0 PROTOCOL SUMMARY

### 1.1 Synopsis

[figure not shown]
| Protocol Synopsis                    |   |
|--------------------------------------|---|
| Protocol Title                       | Ferric Citrate for the Prevention of Renal Failure in Adults with Advanced Chronic Kidney Disease (FRONTIER)  |
| Protocol Number                      | USRC-2021-002   |
| Investigational Product              | Auryxia (Ferric Citrate-KRX-0502)   |
| Reference Therapy, as applicable     | Matching Placebo  |
| Study Population                     | The study population will consist of adult subjects $\geq 18$ years old with a diagnosis of non-dialysis dependent (NDD) advanced chronic kidney disease (CKD)  |
| Number of Study Sites                | Multicenter, up to 25 sites in the United States (US)   |
| Planned Number of Subjects           | Up to 400 subjects will be randomized 1:1 to receive either ferric citrate or matching placebo  |
| Primary Objective/Endpoint           | To determine the effect of ferric citrate on the time to a composite endpoint of initiation of maintenance dialysis or all-cause mortality compared to placebo in adult patients with advanced CKD.   |
| Secondary Objectives/Endpoints       | 

Time to first hospitalization event reported as a serious adverse event (SAE) (excluding disease-related hospitalization [e.g., dialysis access placement, dialysis initiation, kidney transplant] and elective procedures)

Component of Primary – Time to Initiation of Maintenance Dialysis

Component of Primary – Time to All-Cause Mortality

  |
| Methodology (study design)           | Multicenter, randomized, double-blind, placebo-controlled clinical trial to determine the effect of ferric citrate on the time to a composite endpoint of initiation of maintenance dialysis or all-cause mortality in patients with NDD, advanced CKD. Subjects will be randomized in 1:1 ratio to receive either ferric citrate or matching placebo. All subjects will initiate dosing at 2 tablets per meal or snacks, up to 3 times per day (maximum of 6 tablets/day). The dose of ferric citrate/placebo will only be adjusted based on safety/tolerability. Given the double-blind design of this trial, investigators will be instructed to not prescribe commercial Auryxia to either study arm. The study will be considered completed when all randomized subjects have completed their final study visit (Month 9 or EOT) and 30-day safety follow-up visit. Study visits during the treatment period are to be conducted as part of routine scheduled clinical encounters. Standard of care local laboratory results will be collected, including the monitoring of phosphorus and iron indices (TSAT and ferritin) at quarterly intervals. A pregnancy test in women of child-bearing potential will be required. |
| Study Duration                       | Each subject will be followed for a treatment period of approximately 9 months plus an additional 30-day safety follow-up period.   |
| Key Inclusion and Exclusion Criteria | Inclusion Criteria 

Adult patients <math>\geq 18</math> years old.

Diagnosis of NDD advanced CKD, regardless of etiology. Advanced CKD is defined as at least one local laboratory determined estimated glomerular filtration rate (eGFR) <math>\leq 20</math>

  |

|                   |  |
|-------------------|--|
|                   | 
ml/min/1.73m^2 (calculated per any commonly used method or equation for estimating eGFR) within 90 days of Day 1.
 

3. Most recent transferrin saturation (TSAT) ≤45% within 45 days of Day 1.

4. Most recent serum phosphate is ≥3.0 mg/dL within 45 days of Day 1.

5. Most recent ferritin ≤500 ng/mL within 45 days of Day 1.

6. Women of child-bearing potential must have a negative serum or urine pregnancy test within 30 days prior to Day 1 procedures. Can be performed on Day 1 if prior to any Day 1 procedures. Results must be available prior to the 1st dose of study drug.

7. Understands the procedures and requirements of the study and provides written informed consent and authorization for protected health information disclosure.

 |
| Safety Monitoring | All Serious Adverse Events (SAEs) will be collected. Adverse Events of Special Interest (AESI) (iron overload and hypophosphatemia) will also be collected.  |

|  |   |
|--|---|
| 
Statistical considerations
 

a. General analysis plan

b. Rationale for number of subjects

 | 
The primary endpoint is the time to a composite endpoint of initiation of maintenance dialysis or all-cause mortality. The primary endpoint will be analyzed by Cox-proportional hazards regression model. Hazards ratios and corresponding 95% confidence intervals will be presented.
 
The sample size for this study is driven by the primary endpoint, initiation of maintenance dialysis or all-cause mortality and is based on the observed data from the pilot study using nearly identical inclusion and exclusion criteria. The observed rate of the primary composite endpoint in the pilot study (all-cause mortality, maintenance dialysis or kidney transplant) for patients in the standard of care arm was 0.94 events per person-year of follow up. The observed hazard ratio was 0.42 (58% relative risk reduction, <math>p=0.002</math>) for the primary composite endpoint when comparing ferric citrate treated patients versus usual care.
 
Assuming 1 year recruitment and 0.75 years of follow up (9 months) for each individual and a hazard ratio of 0.60 (40% relative risk reduction), a sample size of 400 patients (200 per arm) provides 90% power with a 2-sided alpha <math>p <0.05</math>. Assuming a hazard ratio of 0.50 (50% relative risk reduction), a sample size of 225 patients provides 90% power with a 2-sided alpha <math>p <0.05</math>.
 |
|--|---|

## 1.2 Schema

**Figure 1. Study Schema**

CKD=chronic kidney disease; eGFR=estimated glomerular filtration rate; NDD=non-dialysis dependent; R=randomization; tabs=tablets; TID=three times per day; TSAT=transferrin saturation

### 1.3 Schedule of Activities

**Table 1. Schedule of Activities**

| Study Period  |                        |               | Treatment Period b, c |                         |                         |                       | Follow-up d         |
|---|------------------------|---------------|----------------------------------|-------------------------|-------------------------|-----------------------|--------------------------------|
| Study Month/ Day  | Screening a | Randomization | D1/
Baseline                  | Month 3
(D90)        | Month 6
(D180)       | Month 9
(D270) EOT | Month 10
(EOS)
(Day 300) |
| Visit   | 1                      |               | 2                                | 3                       | 4                       | 5                     | 6                              |
| Visit Window (days)   | -45                    | -8            | 0                                | ±30                     | ±30                     | ±30                   | ±7                             |
| Visit Type  | In-Person              |               | In-person                        | In-person
or virtual | In-person
or virtual | In-person             | virtual                        |
| General and Clinical Assessments                         |                        |               |                                  |                         |                         |                       |                                |
| Informed Consent  | X                      |               |                                  |                         |                         |                       |                                |
| Review inclusion/exclusion                                      | X                      |               |                                  |                         |                         |                       |                                |
| Demographics  | X                      |               |                                  |                         |                         |                       |                                |
| Medical History k                                    | X                      |               |                                  |                         |                         |                       |                                |
| Randomization   |                        | X             |                                  |                         |                         |                       |                                |
| Vital Signs e  | X                      |               | X                                |                         | X                       | X                     |                                |
| Height and Weight f                                  |                        |               | X                                |                         | X                       | X                     |                                |
| Laboratory Assessments as Available per Standard of Care |                        |               |                                  |                         |                         |                       |                                |
| Pregnancy test g                                     |                        | X             |                                  |                         |                         |                       |                                |
| Serum Chemistry   | X a         |               |                                  | X                       | X                       | X i        |                                |
| CBC   | X a         |               |                                  | X                       | X                       | X i        |                                |
| eGFR  | X a         |               |                                  | X                       | X                       | X i        |                                |
| Other laboratory assessments h                       | X a         |               |                                  | X                       | X                       | X i        |                                |
| Serum Phosphorus  | X a         |               |                                  | X                       | X                       | X i        |                                |
| Iron indices  | X a         |               |                                  | X                       | X                       | X i        |                                |
| Safety Assessments                                       |                        |               |                                  |                         |                         |                       |                                |
| Concomitant medication review j                      | X                      |               | X                                | X                       | X                       | X                     |                                |
| PRBC transfusions and/or dialysis access procedures             | X                      | ←————→        |                                  |                         |                         |                       |                                |
| Adverse Events of Special Interest n                 |                        |               | ←————→                           |                         |                         |                       |                                |
| SAE Assessment l                                     |                        |               | ←————→                           |                         |                         |                       |                                |
| Endpoint Assessment o                                |                        |               |                                  | X                       | X                       | X                     | X                              |
| Study intervention                                       |                        |               |                                  |                         |                         |                       |                                |
| Study drug prescription/provide study drug m         |                        | X             | X p                   | X                       | X                       |                       |                                |
| Study drug accountability q                          |                        |               |                                  |                         | X                       | X                     |                                |

| Study Period        |                        |               | Treatment Period b, c |                         |                         |                       | Follow-up d         |
|---------------------|------------------------|---------------|----------------------------------|-------------------------|-------------------------|-----------------------|--------------------------------|
| Study Month/ Day    | Screening a | Randomization | D1/
Baseline                  | Month 3
(D90)        | Month 6
(D180)       | Month 9
(D270) EOT | Month 10
(EOS)
(Day 300) |
| Visit               | 1                      |               | 2                                | 3                       | 4                       | 5                     | 6                              |
| Visit Window (days) | -45                    | -8            | 0                                | ±30                     | ±30                     | ±30                   | ±7                             |
| Visit Type          | In-Person              |               | In-person                        | In-person
or virtual | In-person
or virtual | In-person             | virtual                        |

CBC: complete blood count; D: Day; eGFR: estimated glomerular filtration rate; EOT: end of treatment; ET: early termination; PRBC: packed red blood cell; PTH: parathyroid hormone; SAE: serious adverse event; SOC: standard of care; TSAT: transferrin saturation.

A: Laboratory Assessments used for screening eligibility must be within 45 days prior to Day 1 with the exception of eGFR which must be within 90 days of Day 1. The screening visit may be conducted as part of a routine scheduled clinical encounter.

B: Study visits are scheduled to occur every 90 days +/-30 days during the treatment period and are anticipated to be conducted as part of a routine scheduled clinical encounter.

C: Virtual visits may be conducted via telephone or electronic format (i.e., zoom call) and will be documented in source documents.

D: Subjects will conclude the study with a follow-up virtual visit 30 days after their last dose of study drug to assess for SAEs and vital status.

E: Vital signs will include systolic blood pressure, diastolic blood pressure, and resting heart rate. These may be captured using data from the subject's clinical encounter. If SOC vital signs are collected prior to signing of informed consent at the screening visit, those vital signs may be captured and do not need to be repeated.

F: Both height and weight will be collected at the Day 1 visit. Height may be self-reported. Weight only will be collected during the treatment period and may be captured using data from the clinical encounter.

G: Serum or urine pregnancy test (women of childbearing potential) must be done at any point within 30 days of Day 1. Can be performed on Day 1 if prior to any Day 1 procedures. Results must be available prior to the 1st dose of study drug.

H: Other laboratory assessments include urine chemistry, hepatic panel, magnesium, cystatin-C and PTH if available (section 9.4, Table 2).

I: The most recent laboratory assessments prior to EOT will be utilized

J: Routine concomitant medications will be assessed at each in-person visit (Screening, Day 1, Month 9). Concomitant medications of interest will be assessed at Screening at then at each subsequent study visit (see Section 9.5.1).

K: Targeted medical history (refer to section 9.2.1)

L: Collection begins at initiation of study drug treatment (1st dose of study drug) and continues through the follow-up visit. Refer to Section 9.5.2.

M: Prescription for study drug must be sent to USRC Rx Pharmacy for processing at time of randomization to ensure on-time delivery prior to Day 1. Refill prescriptions or changes to prescription will be sent to the pharmacy as needed. Dispensing will be a minimum of 3 months supply.

N: Collection begins at initiation of study drug treatment (1st dose of study drug) and continues through the follow-up visit. Refer to Section 9.5.2.

O: Endpoint assessment includes initiation of dialysis, vital status (alive or deceased), transplant, and hospitalization. Any subject who either receives a kidney transplant or initiates maintenance dialysis, and has not withdrawn consent from study participation, will have a vital status check performed at 30-days following the relevant event.

P: If there are delays related to shipment from the USRC Rx pharmacy, study drug will be provided to subjects within 12 days of the Day 1 visit.

Q: Study drug accountability is performed at in-person visits only.

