### 5.4 End of Study Definition

A participant is considered to have completed the study if he or she has completed all phases of the study including the last visit or the last scheduled procedure shown in the Schedule of Activities (SoA) (Section 1.3).

The end of the study will be considered complete after all randomized subjects have completed their final study visit (Month 9 or EOT) and 30-day safety follow-up visit.

Any subject who either receives a kidney transplant or initiates maintenance dialysis, and has not withdrawn consent from study participation, will have a vital status check performed at 30-days following the relevant event. The vital status check will ascertain the subject's mortality (alive vs. deceased).

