### **7.5.3 Erythropoiesis-Stimulating Agents (ESAs) or Packed Red Blood Cell (PRBC) Transfusion**

There are no restrictions on the use of ESA and dose adjustments may be made at the discretion of the Investigator. All changes in ESA therapy will be captured in source documentation and in the eCRF

Receipt of RBC transfusions will be captured in source documentation and in the eCRF.

- Subjects who receive repeated red blood cell transfusions during the study may need to temporarily hold study drug. For the purpose of the study, “repeated blood transfusion” will be defined as receipt of >4 units of red blood cells within any 6-month period of time. Prior to study drug hold please contact the medical monitor. If study drug is permanently discontinued, subsequent study visits including the Follow Up visit (Visit 6) should occur per the SoA.

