### **8.1.2 Permanent Discontinuation of Study Drug**

Subjects are free to withdraw from taking study drug at any time upon request. Subjects who permanently discontinue study drug will be asked to continue study participation (either by in person visits or by allowing access to medical records) in accordance with the SoA, through completion of the study. The endpoint assessment will be considered the End of Study date.

If a subject declines to continue study visits and withdraws consent to be followed, the subject is an early termination, and NO endpoint assessment will be performed. The subject's early termination date will be considered the End of Study date.

An Investigator **may** discontinue study drug or withdraw a subject from the study for the following reasons:

- Pregnancy
- Significant study intervention non-compliance
- If any clinically significant AE, laboratory abnormality, or other medical condition or situation occurs such that continued participation in the study would not be in the best interest of the subject
- Iron overload supported by liver biopsy, magnetic resonance imaging and persistent elevations in TSAT or ferritin
- If the TSAT remains >50%; Refer to Section 7.1.2.1
- If the ferritin remains >500 ng/mL; Refer to Section 7.1.2.1
- If the serum phosphorus remains <3.0 mg/dL; Refer to Section 7.1.2.1
- Investigator-Sponsor decision
- Lost to follow-up

The reason for study drug discontinuation will be recorded in source documentation and in the eCRF.

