### **9.1.4 Month 10/End of Study (EOS)**

There is a 30-day safety follow-up visit after the Month 9 visit which will be performed via a telephone call/virtual visit.

Any subject who either receives a kidney transplant or initiates maintenance dialysis, and has not withdrawn consent from study participation, will have a vital status check (alive or deceased) performed at 30-days following the relevant event.

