#### **9.6.5    Reporting Period**

SAE and Adverse Events of Special Interest collection will begin from initiation of study drug treatment through the 30-day follow-up visit. Subjects will be followed for protocol required SAEs and Adverse Events of Special Interest until the final required protocol visit or until all drug-related toxicities and Adverse Events of Special Interest and SAEs have resolved (or are considered chronic/stable), whichever is later.

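### Schedule footnote D ends the study 30 days after the last dose, which contradicts the rules that keep early drug stoppers in follow-up through Visit 6 (Month 10)

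*Protocol*

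**What the plan says.** Footnote D is attached to the Follow-up column of Table 1 (protocol 1.3) and reads: "Subjects will conclude the study with a follow-up virtual visit 30 days after their last dose of study drug". The column itself is headed Month 10, End of Study, Day 300, with a window of ±7 days.

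The body of the protocol ties the closing visit to the calendar and not to the last dose:

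- Section 9.1.4: "There is a 30-day safety follow-up visit after the Month 9 visit".
- Section 8.1.2: "Subjects who permanently discontinue study drug will be asked to continue study participation", following the Schedule of Activities until the study is complete. It adds: "The endpoint assessment will be considered the End of Study date".
- Section 7.5.3, on permanent discontinuation after repeated transfusions: "subsequent study visits including the Follow Up visit (Visit 6) should occur per the SoA". Section 7.5.4 says the same for subjects who leave study drug because commercial product is continued.
- Section 7.1.2.1 continues visits, including Visit 6, when drug is held again for TSAT or ferritin after a dose reduction.

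Section 5.4 defines the end of the study by all subjects having "completed their final study visit (Month 9 or EOT) and 30-day safety follow-up visit". Section 9.6.5 states: "SAE and Adverse Events of Special Interest collection will begin from initiation of study drug treatment through the 30-day follow-up visit".

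On analysis, protocol 10.3 and SAP 3.3 both use endpoint data collected after drug discontinuation. SAP 3.3 also caps the 10-month visit at 307 days from study drug Day 1.

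**The concern.** The footnote and the body rules give the same date only for subjects who take drug up to Month 9. For anyone who stops earlier they differ by the length of the off-drug period. The body rules do not settle the matter by themselves, because 7.1.2.1, 7.5.3, 7.5.4 and 8.1.2 all send the site back to the Schedule of Activities, where footnote D says something else. Section 8.1.2 also names an unspecified endpoint assessment as the End of Study date, although the schedule has four (Months 3, 6, 9 and 10).

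At stake are data that no analysis can recover. The plan wants a comparison that counts events whatever the drug status. If early stoppers were closed 30 days after the last dose, their part of the comparison would become on-treatment plus 30 days. The first secondary endpoint is exposed too, because it counts hospitalisations reported as SAEs and the site would no longer be in contact to record them.

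**Working it through.** **The conflict in one subject.** Drug is stopped for good on Day 60.

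- Footnote D: 60 + 30 = Day 90.
- Table 1 column and 8.1.2: Day 300.
- Gap: 300 − 90 = 210 days.

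The design rates are 0.94 per person-year on control and 0.94 × 0.60 = 0.564 on ferric citrate (protocol 10.1). The chance of a primary event in the gap, for a subject event-free at Day 90, is:

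- control: 1 − exp(−0.94 × 210/365.25) = 0.42
- ferric citrate: 1 − exp(−0.564 × 210/365.25) = 0.28

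**The plan's own sample size.** Inputs are those rates, 0.75 years of follow-up, HR 0.60, 400 subjects allocated 1:1, and two-sided alpha 0.05.

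- Event probability, control: 1 − exp(−0.94 × 0.75) = 0.506
- Event probability, ferric citrate: 1 − exp(−0.564 × 0.75) = 0.345
- Average 0.4254, so expected events = 400 × 0.4254 = 170
- Events for 90% power (Freedman): (1.960 + 1.282)² × (1.6/0.4)² = 168.1, taken as 169. N = 169/0.4254 = 398 after rounding up, which reproduces the stated 400.
- Power at 170 events (Schoenfeld): Φ(√(170.2/4) × |ln 0.60| − 1.96) = 0.915. Freedman gives 0.903.

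**Effect of applying footnote D to every early stopper.** The documents give no discontinuation rate, so the proportion q stopping by Month 9 is an assumption. Stop times are taken as exponential with rate μ = −ln(1 − q)/0.75, equal in both arms, with the hazard unchanged after stopping. Expected events per arm are 200 × ∫ λ exp(−λt) G(t) dt over 0 to 0.75 years. Here G(t) = 1 up to 30 days and exp(−μ(t − 30 days)) afterwards.

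| q (assumed) | Events | Lost | Power, Schoenfeld | Power, Freedman |
|---|---|---|---|---|
| 0 | 170 | – | 0.915 | 0.903 |
| 10% | 164 | 6 (4%) | 0.905 | 0.893 |
| 20% | 158 | 12 (7%) | 0.894 | 0.881 |
| 30% | 151 | 19 (11%) | 0.881 | 0.867 |

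If events are counted to Day 300 instead, full follow-up gives 182 events. The losses are then about 4, 8 and 12%, and the fall in power is again about 1, 2 and 3 points.

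**Effect on the hazard ratio.** A simulation to Day 300 used stop times spread evenly over Days 0 to 270, with an assumed 30% stopping on ferric citrate and 10% on placebo.

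- Hazard unchanged after stopping: the rate ratio is 0.60 with full follow-up and 0.60 with truncation.
- Hazard 1.5 times higher after stopping: 18 of 188 events are lost, and the rate ratio moves from 0.63 (full) to 0.61 (truncated).

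Unequal stopping alone therefore does not move the estimate. A change in prognosis after stopping is also needed.

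**The case against.** The strongest reply is that the intended design is clear and that one general footnote would have to be placed above several specific rules before any data were lost. Much of this stands. Sections 8.1.1 and 10.3 both separate stopping drug from leaving the study. Sections 7.1.2.1, 7.5.3, 7.5.4 and 8.1.2 keep off-drug subjects in follow-up. The SAP dates the 10-month visit from Day 1: 300 + 7 = 307. What remains is that those rules refer the site to the schedule, and the schedule's own note gives the other date.

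The reply also limits how far the point can be taken. A reader might infer four stronger things that the documents do not support.

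- *That 5.1 and 5.4 also anchor follow-up to the last dose.* Table 1 and 9.1.3 place EOT at the Month 9 visit. Thirty days after EOT in 5.1 is then Day 300, and 5.4 is at most ambiguous. Only footnote D uses the last dose.
- *That 9.6.5 independently cuts off SAE collection.* Its next sentence continues follow-up to the final required visit or to resolution, whichever is later. The exposure arises only if footnote D is used to fix that final visit.
- *That high TSAT, high ferritin or low phosphorus will end follow-up sooner on ferric citrate.* These trigger temporary holds, and a hold is not a last dose. Permanent discontinuation for persistent values is optional under 8.1.2.
- *That the pooled anaemia data show unequal stopping.* The 75.3% and 61.7% in 3.3.1 are the incidence of any treatment-emergent event, not discontinuation rates.

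**Conclusion.** Footnote D is wrong as written for subjects who stop study drug early, and it should be corrected. The contradiction is textual and does not depend on the arithmetic.

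The size is modest: about 4 to 11% of primary events and 1 to 3 points of power. That rests on an assumed 10 to 30% stopping and on every early stopper being closed under the footnote, so it is the upper end for each stop rate. If sites follow the body text, nothing is lost.

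A material bias in favour of ferric citrate is not shown. The only shift found (0.63 to 0.61) needs unequal stopping, a higher hazard after stopping and universal literal use of the footnote, all at once, and the documents supply none of these. SAP 3.3 also caps vital status at 37 days after early termination. That would matter here only if a drug stop were coded as early termination, a term that 8.1.2 applies to subjects who decline further follow-up.

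Subjects who start maintenance dialysis or receive a transplant leave by design with a 30-day vital status check, and are outside this point.

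**What to change.** - **Footnote D:** state that Visit 6 takes place at Month 10 (Day 300 ±7 from Day 1, in line with the SAP cap of 307 days) whether or not the subject is still taking study drug. The exceptions are those the protocol already has: death, maintenance dialysis or kidney transplant with the 30-day vital status check, withdrawal of consent, loss to follow-up, or early termination as defined (which covers never-dosed subjects).
- **Section 8.1.2:** specify the final (Month 10) endpoint assessment as the End of Study date.
- **Section 5.4:** clarify that EOT means the Month 9 visit.

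Sections 5.1 and 9.6.5 and SAP 2.1 need nothing beyond consistency with that definition.

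The footnote should use the day count and not the actual date of the Month 9 visit. That visit has a window of ±30 days, so 30 days after it can fall anywhere from Day 270 (240 + 30) to Day 330 (300 + 30). This mismatch with the ±7 window of Visit 6 is already in the schedule. The sponsor should confirm at the same time how a late Month 9 visit is handled.

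The cost is wording in an amendment or site memo. The visits already exist in the schedule. The one downside is continued contact with subjects who are off drug, which 8.1.2 already asks for.
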